4. Differences in rates of treatment reach, retention, and completion by patient factors (demographics, nicotine dependence, smoking history). (Aim 5).
5. Moderation of treatment effects (high- vs. low-intensity) by patient factors. (Aim 5).

PROTOCOL TITLE: Comparative Effectiveness Trial of Tobacco Cessation Treatments among Cancer Patients who Smoke

6. Health outcomes (e.g., cancer mortality, cancer progression, new cancer diagnoses, treatment side effects).

3.5 Primary safety endpoints.

1. Adverse events, by treatment condition.
2. Serious adverse events, by treatment condition.

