11.0 Study Intervention

PROTOCOL TITLE: Comparative Effectiveness Trial of Tobacco Cessation Treatments among Cancer Patients who Smoke

11.1 Description.

The outreach strategy that is being evaluated in terms of reach and reach equity comprises mailings (no more than quarterly) and proactive telephone calls offering smoking treatment information and access.

The smoking cessation treatment strategies being evaluated in terms of comparative effectiveness, efficiency, and equity are 2 treatment packages that vary in terms of intensity, cancer-specificity, costs, and burden on patients. These interventions are described below.

- Standard treatment
 - 3 counseling calls (each 10-15 minutes in length) on the following schedule (an outline of the counseling protocol is uploaded with the application):
 - Pre-quit call (1 week before the target quit date they selected at enrollment)
 - Post-quit call 1 (target quit date or next day)
 - Post-quit call 2 (1 week after the target quit date).
 - Nicotine patch starter kit (1 14-count box of transdermal nicotine patches) for use starting on the target quit date, at the following dosing schedule (medication instructions to be mailed to participants are uploaded with the application):
 - For those who smoke 10 or more cigarettes per day at enrollment, 21-mg patches.
 - For those who smoke 5-9 cigarettes per day, 14-mg patches.
 - For those who smoke 1-4 cigarettes per day, 7-mg patches.
 - Those who smoke less frequently than daily will not be eligible for patches.
 - Those whose clinicians disapprove of nicotine patch therapy for their patients will not receive patches.
 - Mailed information about smoking cessation treatments available from the Wisconsin Tobacco Quit Line (or state quit line in patient's state of residence) and SmokefreeTXT, two publicly funded, remotely delivered treatment services available to the general public.
- Enhanced treatment
 - 7 counseling calls (each 10-15 minutes in length) on the following schedule (an outline of the intensive counseling protocol is uploaded with the application):
 - Pre-quit call (1 week before the target quit date they selected at enrollment).
 - Post-quit call 1 (target quit date or next day).
 - Post-quit call 2 (1 week after the target quit date).

PROTOCOL TITLE: Comparative Effectiveness Trial of Tobacco Cessation Treatments among Cancer Patients who Smoke

- Post-quit call 3 (2 weeks after the target quit date).

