- Post-quit call 4 (4 weeks after the target quit date).
- Post-quit call 5 (8 weeks after the target quit date).
- Post-quit call 6 (12 weeks after the target quit date).
- Varenicline starting 7 days before the target quit date (0.5 mg once per day for 3 days, 0.5 mg twice per day for 4 days, 1 mg twice per day for 11 weeks), as per the package insert (medication instructions for patients are uploaded with the application). Those who smoke less frequently than daily will not be eligible for varenicline.
 - If patients in high-intensity treatment are ineligible for varenicline (due to contraindications reported at initial medication screening or clinician disapproval of varenicline for the patient), patients will instead be offered 12 weeks of nicotine patch therapy for use starting on the target quit date, at the following dosing schedule:
 - For those who smoke 10 or more cigarettes per day at enrollment, 21-mg patches (week 1-8), 14-mg patches (week 9-10), 7-mg patches (week 11-12).
 - For those who smoke 5-9 cigarettes per day, 14-mg patches (week 1-10), 7-mg patches (week 11-12).
 - For those who smoke 1-4 cigarettes per day, 7-mg patches.
 - Those who smoke less frequently than daily will not be eligible for patches.
 - Those whose clinicians disapprove of nicotine patch therapy for their patients will not receive patches.
- Mailed information about smoking cessation treatments available from the Wisconsin Tobacco Quit Line (or state quit line in patient's state of residence) and SmokefreeTXT, two publicly funded, remotely delivered treatment services available to the general public. These information sheets are uploaded with the application.

11.2 Drug/Device Handling.

- Study medications (nicotine patches, varenicline) will be received at the Center for Tobacco Research and Intervention by the Study Coordinator or designees in the Madison office.
- Nicotine patches will arrive in commercially packaged boxes of 14 patches each (two weeks of 21mg, 14mg, or 7 mg patches).

PROTOCOL TITLE: Comparative Effectiveness Trial of Tobacco Cessation Treatments among Cancer Patients who Smoke

- Varenicline will arrive in commercially packaged 28-day starter packs that clearly designate when and how to start the medication run-in period (beginning 1 week before the target quit day), or 28-day continuation packs (standard commercial packaging sizes).

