Adverse Event Assessment (all participants will be assessed through 26 weeks post-target-quit date; those in enhanced care will have additional assessments at counseling contacts specific to that arm)		✓	✓	✓	EC	EC	EC	✓	✓	✓
Biochemical verification via CO and urine cotinine (or mailed saliva cotinine)										✓

✓ = applies to both treatment arms

SC = applies only to standard care arm

EC = applies only to enhanced care arm

13.3 Research procedures:

1. Safety monitoring and risk prevention.

To reduce risks to CET participants, we will first screen them for eligibility prior to enrollment, will ask their clinicians to review and disapprove study medications that raise safety concerns for them, and then we will monitor for adverse events at all study contacts following the initiation of smoking cessation treatments in the trial. The schedule for these activities is presented above. Please note that follow-up contacts will occur for all study participants 12 and 26 weeks after their target quit date (i.e., after the end of pharmacotherapy in both conditions, which will end 2 weeks after a target quit date in the control condition and 11 weeks after the target quit date in the enhanced care condition for varenicline). The final counseling contact in the enhanced care condition will also occur at the 12-week post-quit time point.

PROTOCOL TITLE: Comparative Effectiveness Trial of Tobacco Cessation Treatments among Cancer Patients who Smoke

For qualitative interviews, interviewers will monitor for distress or confusion during the interview and will stop the interview and address the distress or confusion, as needed.

2. Biospecimens.

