persistent or significant disability/incapacity, or involve congenital abnormality/birth defects. Unanticipated problems will be monitored and reported to the DSMC. The assessment of adverse events will occur via phone calls at all study contacts that occur after the initiation of treatment (study contacts 2 through 11). Adverse events are events that meet the following criteria: 1) suggest the research places subjects or others at increased risk of harm, 2) are unexpected (in terms of nature, severity or frequency) given the research procedures that are described in the study-related documents, and 3) possibly related to study participation. Any SAE will be queried and reported if it meets the definition of an unanticipated problem. All study-related adverse events will be assessed in a timely manner so that NIH, FDA, and the IRB may be notified, as needed. Adverse event assessment, recording, reporting, and investigation will be accomplished through staff training, structured/standardized assessments of untoward occurrences/events, and regular monitoring by the study team. Also, any adverse event that affects the patient's ability to receive cancer therapy will be reported to his or her oncologic care team as soon as possible. The Lead Researcher and PI has ultimate responsibility for ensuring that SAEs are reported in a timely manner. Additionally, the IRB will receive an annual report of all SAEs and AEs meeting the criteria listed above.

2. **Safety data, untoward events, and efficacy data review.** The study team will continuously monitor adverse event data collected using a standardized prompt in contacts 2-11 in the CET, and any adverse event data that come to light at other times (e.g., if a patient or oncologist reports a health event). The study team will review this information no less often than monthly and the DSMC will review these data at least twice per year.
3. **Safety data collection.** Adverse event data will be collected during phone contacts and the final biochemical verification visit.
4. **Frequency of data collection.** In the CET, safety data will be collected from study contact 2 (approximately 1 week prior to a participant's target quit date) through the final study visit (study contact 11, approximately 6 months after the participant's target quit date).
5. **Who will review the data.** Safety data will be reviewed by the Lead Researcher, study physician, and the DSMC.

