PROTOCOL TITLE: Comparative Effectiveness Trial of Tobacco Cessation Treatments among Cancer Patients who Smoke

6. **The frequency of review of cumulative data.** The Lead Researcher and study team will review all adverse event data as they are collected. The study physician will review any adverse events that are unanticipated, severe, and possibly related to study procedures, and all serious adverse events among CET participants, as they occur. The DSMC will review cumulative data no less than twice per year.
7. **Analyzing safety data.** Given the modest sample size in this pilot study, we will focus on effect sizes rather than tests of significance when comparing adverse event rates in the two CET conditions. Any unanticipated or serious adverse events in either condition will be thoroughly assessed and examined.
8. **Conditions that trigger immediate suspension of the research.** The CET will be suspended immediately if data suggest there are unanticipated, severe problems associated with treatment in the CET. The NIH will be notified within 5 days if the PI deems it necessary to suspend the study. In the case of a temporary suspension, the PI will develop a plan for continuation of the study and discuss this plan with NIH in a reasonable time frame.
9. **How the study team will adhere to reportable event reporting requirements.** Any reportable events that are unexpected, immediately life-threatening or severely debilitating, and probably caused by study medication will be reported within 1 business day. If new information about study medication risks that was not previously known to investigators or participants is discovered, investigators will prepare a change of protocol with revised study documents or withdraw affected drugs from the protocol within 14 business days. Likewise, the research team will report to the IRB within 14 business days any of the following: failures to obtain properly informed consent for the CET; dosing errors in medication dispensing; unexpected harms to participants or others that are probably related to the study procedures; noncompliance that could affect participants' rights, welfare, or safety; reportable audit findings; breach of confidentiality; failure to suspend study activities during a participant's known incarceration; and unresolved participant complaints. Breaches of confidentiality of PHI will also be reported to the HIPAA privacy officer.

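### Adverse events are prompted at weeks 2, 4 and 8 in enhanced care only, and the by-arm comparison of event rates makes no allowance for it

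*Combined protocol and SAP*

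**What the plan says.** The adverse event row of the schedule (section 13.2) marks contacts 2 to 4 (weeks -1, 0 and 1) for both arms. It marks contacts 5 to 7 (weeks 2, 4 and 8) EC, and the follow-ups at weeks 12 and 26 for both arms again. The key reads "EC = applies only to enhanced care arm", and the row label says that "those in enhanced care will have additional assessments at counseling contacts specific to that arm".

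The call lists in section 11.1 agree. The last standard-care call is "Post-quit call 2 (1 week after the target quit date". Enhanced care continues with "Post-quit call 3 (2 weeks after the target quit date", "Post-quit call 4 (4 weeks after the target quit date", and further calls at weeks 8 and 12.

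The row also marks the final visit (contact 11, weeks 26-29). Section 13.3 (Biospecimens) ties that visit to participants who report no tobacco use at the 26-week call.

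Section 3.5 makes "Adverse events, by treatment condition" a primary safety endpoint, with serious adverse events alongside. Section 23.1 item 7 says "we will focus on effect sizes rather than tests of significance when comparing adverse event rates in the two CET conditions". Section 20.4 includes side effects among the binary outcomes to be modelled on condition by logistic regression. No section states a recall period for the prompt, limits the comparison to contacts that both arms have, or otherwise deals with the difference in prompting.

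**The concern.** A safety comparison between arms is interpretable only if events are looked for in the same way in both. Here enhanced care is asked three extra times in the stretch where standard care is not asked at all. Minor events that fade from memory within a few weeks have a better chance of being recorded in enhanced care. Reporting effect sizes in place of tests does not help, because the distortion is in the estimate itself.

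The extra prompts also fall where drug exposure differs. Section 13.3 has patches ending 2 weeks after the quit date in standard care and varenicline ending at week 11 in enhanced care. In that stretch a real drug effect and a prompting effect cannot be told apart.

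The comparison has consequences. Section 20.5 has safety data examined throughout for signs that a condition is causing harm, with referral to the DSMC and IRB. Section 2.1 has the pilot estimates informing a full-scale trial.

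**Working it through.** The plan gives no adverse event rate or power for the safety comparison, so there is no figure of its own to reproduce. The check asks what share of events each arm would record if true rates were equal and constant from week -1 to week 26 (27 weeks).

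**Inputs from sections 11.1, 13.2 and 4.3**

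- Standard care: prompts at -1, 0, 1, 12, 26 (5 prompts); gaps 1, 1, 11, 14 weeks.
- Enhanced care: prompts at -1, 0, 1, 2, 4, 8, 12, 26 (8 prompts); gaps 1, 1, 1, 2, 4, 4, 14 weeks.
- 25 participants per arm.
- Contact 11 is left out. The two week-12 contacts in enhanced care are counted once: the extracted row does not show whether both carry a prompt, and being in the same week they do not change the result.

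**Assumed recall models**

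(a) Fixed look-back of w weeks: capture = sum of min(gap, w) / 27.

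(b) Forgetting with half-life h weeks, λ = ln 2 / h: capture = sum of (1 − exp(−λ·gap)) / λ, divided by 27.

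| Model | Standard | Enhanced | Ratio |
|---|---|---|---|
| Look-back 1 week | 4/27 = 0.148 | 7/27 = 0.259 | 1.75 |
| Look-back 2 weeks | 6/27 = 0.222 | 11/27 = 0.407 | 1.83 |
| Look-back 4 weeks | 10/27 = 0.370 | 17/27 = 0.630 | 1.70 |
| Look-back 11 weeks | 24/27 = 0.889 | 24/27 = 0.889 | 1.00 |
| Since last contact, perfect recall | 27/27 | 27/27 | 1.00 |
| Half-life 4 weeks | 0.445 | 0.573 | 1.29 |
| Half-life 8 weeks | 0.634 | 0.725 | 1.14 |
| Half-life 16 weeks | 0.785 | 0.841 | 1.07 |
| Half-life 52 weeks | 0.926 | 0.945 | 1.02 |

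Up to week 12 only (13 weeks), the ratio is 2.00, 2.25 and 2.17 for look-backs of 1, 2 and 4 weeks, and 1.51, 1.27 and 1.14 for half-lives of 4, 8 and 16 weeks.

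**Chance.** Take event counts as Poisson with mean 25 × m × capture, where m is the assumed number of true events per person. At m = 1 and a 4-week half-life, the expected counts are 11.1 (standard) and 14.3 (enhanced), and enhanced care shows the larger count with probability 0.70. Over m = 0.5 to 4 that probability is 0.62 to 0.89 at a 4-week half-life, 0.56 to 0.77 at 8 weeks and 0.48 to 0.54 at 52 weeks.

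**A check on the remedy.** Suppose the comparison were restricted to shared contacts while each prompt asked only about the time since the last contact. Enhanced-care events from weeks 1 to 8 would then drop out. Its capture would be (1 + 1 + 4 + 14)/27 = 20/27 = 0.74, against 1.00 in standard care, which reverses the bias. If the week-12 prompt covers the whole period since week 1 in both arms, the gaps are 1, 1, 11, 14 in both, and the ratio is 1.00 under every model above.

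**The case against.** The recall period may well be written into the surveys uploaded with the application, which are not in these documents. If each prompt asks about everything since the last contact and recall is good, the bias is small or absent. This stands, and it is why the size can only be given as a range.

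A reader might infer that enhanced care is bound to show more events, with a spurious odds ratio of about 1.7 to 2.7. Those figures come from treating every prompt as equally productive: 1 − (1 − p)^k, with k = 5 against 8 or 9. At p = 0.05 and k = 8 this gives 22.6% against 33.7%, odds ratio 1.74; at p = 0.15 and k = 9 it gives 2.65. The model lets a prompt covering 11 weeks yield no more than one covering a single week, its upper end counts week 12 twice, and the documents supply no value of p. With the forgetting model and 0.5 to 2 true events per person, the odds ratio for any recorded event is 1.33 to 1.50 at a 4-week half-life and 1.17 to 1.28 at 8 weeks.

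Section 23.1 also defines adverse events narrowly, as unexpected, suggesting increased risk, and possibly related. Read literally, that excludes the known side effects listed in section 22.1. It would lower the counts in both arms but would not equalise the prompting, and section 20.4 plans to model side effects in any case.

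This is also a small pilot, the extra checks during longer drug exposure are deliberate and openly stated, and events that surface at other times are monitored too. All true, and good reason to keep the extra prompts. None of it makes the two arms' counts comparable.

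Finally, one might see a contradiction in section 23.1, which has adverse events assessed at every contact from 2 to 11, although standard care has no contacts 5 to 8. The schedule key shows which contacts each arm has, so this is a matter of wording only.

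**Conclusion.** The point holds as an expected bias of unknown size. Nothing in the plan handles the unequal prompting, and under every imperfect-recall model examined, apart from a look-back long enough to span the 11-week gap, the bias runs towards more recorded events in enhanced care. The capture ratio is 1.00 with complete recall since the last contact, 1.07 to 1.29 for half-lives of 16 to 4 weeks, and 1.70 to 1.83 for look-backs of 1 to 4 weeks. These figures assume equal and constant true rates and the same recall behaviour in both arms.

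The documents do not support saying that enhanced care will show more events: with 25 per arm, chance may hide or reverse the effect. Nor should an excess be put down to varenicline as such, since sections 6.2 and 11.1 allow some enhanced-care participants to receive patches or no study drug. Serious events are probably less affected, being better remembered and more likely to surface by other routes; that is a judgement. The contact 11 prompt is a smaller problem of the same kind, because who receives it depends on reported abstinence.

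**What to change.** In sections 3.5 and 23.1 item 7:

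- Base the between-arm effect size on the contacts that both arms share (weeks -1, 0, 1, 12 and 26).
- State the recall period. Have the week-12 and week-26 follow-up prompts ask both arms about the same fixed look-back. At week 12 this is the whole period since week 1, including anything enhanced-care participants already reported at weeks 2 to 8. Without this step the restriction would introduce the reverse bias shown above.
- Report the full event count by arm and contact alongside, labelled as subject to unequal ascertainment. List separately the events found only at enhanced-only calls or at contact 11.
- For serious events, use the EHR extract already planned for participants in both arms (sections 13.1 and 17.4) as a supporting common source, noting that care outside the health system may be missed.
- Keep every extra prompt for individual safety monitoring.
- In section 23.1, say that the range of contacts applies as each arm has them.

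The cost is protocol and analysis wording, plus a slightly longer recall question at week 12. The effect size loses some sensitivity to mid-treatment events, but these stay visible in the full count.
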